# 3.5.2 Clinical Results: US Phase I Trials

The Division of Cancer Treatment and Diagnosis, National Cancer Institute sponsored two phase I trials of perifosine evaluating a loading dose followed by daily maintenance dose schedule. A loading dose/daily maintenance schedule was proposed due to improved efficacy in several preclinical cancer models with this schedule and the fact that daily doses alone required some days (and possible more than a week) to reach steady state plasma levels. A loading dose could potentially achieve active anti-tumor serum concentrations followed by tolerable daily maintenance dosing. Since both preclinical studies and the earlier phase I studies had suggested that increases in plasma levels were not linear after a threshold that might be about 400 mg, the loading dose was fractionated and administered every 6 hours to improve bioavailability and decrease Cmax. It was also anticipated that by lowering Cmax toxicities such as emesis might be decreased. In both studies, patients received antiemetic prophylaxis with dexamethasone and 5HT3 antagonist before initial loading dose. Similar to the results from the Asta Medicasponsored studies, the most frequently observed toxicities in NCI sponsored phase I studies were gastrointestinal (nausea, vomiting, diarrhea) and fatigue. Chronic nausea among patients receiving perifosine appears to resolve approximately 48 hours following discontinuation of therapy. In contrast, fatigue may persist for weeks after therapy has ended.

## Phase I evaluation of the "Intermittent Schedule" at the NCI

The first trial examined a loading dose on day 1 followed by a maintenance dose schedule for 20 days in patients with solid tumors repeated every 28 days. (Because of the 7 day intervals without drug, this has been referred to as the "intermittent schedule.") In an attempt to minimize nausea, doses were administered with meals or, with maintenance doses, at bedtime. In addition, prior to the initial loading dose, patients were given granisetron, metoclopramide, diphenhydramine, and dexamethasone as antiemetic prophylaxis. Thirty-one patients were treated on this study. Gastrointestinal toxicities were dose limiting. Dose limiting nausea and vomiting despite antiemetic prophylaxis occurred with loading doses of 1200-1500 mg. Grade 3 arthralgias and arthritis in the form of gout or pseudo-gout were seen in two patients taking perifosine 200 mg/day. One patient with a history of gout had reappearance of gout and one patient without a prior history had an episode of pseudogout. One patient with a history of hyperuricemia, had grade 2 episodes of gout. Persistent grade 2 nausea and vomiting despite antiemetics and fatigue occurred with a maintenance dose of 200 mg/day. The maximum tolerated dose (MTD) and recommended phase II dose (RP2D) were established as: Cycle 1: 900/150 mg loading/maintenance dose and for

# IRB#: 06-044 A(11)

subsequent cycles: 300/150 mg loading/maintenance dose ([19]). The day 1 loading dose was divided into 2 equal doses of 450 mg taken with food, 6 hours apart on day 1. Among 11 patients treated at the MTD/RP2D, no patients experienced grade 3-4 dose limiting events during the loading dose or maintenance dose periods in the first cycle. Only one other grade 3 toxicity, infection without neutropenia, felt to be probably due to the drug was recorded at dose level III. Grade 1-2 fatigue occurred in 8/11 patients and grade 2 gastrointestinal toxicity was intermittent and tolerable.

Gastrointestinal toxicities experienced on this trial are summarized in the following table:

Table 5

NCI Trial I - A Phase I Trial of Oral Perifosine with Different Loading/ Maintenance Doses using the "Intermittent Schedule" in Patients with Refractory Neoplasms

Dose		Patients	atients Maximum intensity (CTC grade) during any treatment course								se			
Level	Dosage - Cycle 1	Treated		Na	usea			Vor	niting	5	Diarrhea			
	(Loading /													
[mg/wk]	Maintenance)		0	Ι	II	III	0	Ι	II	III	0	Ι	II	III
Ι	300 mg/50 mg	3		2				1				1	1	
II	600 mg/100 mg	2		2				1	1			1	1	
IIA	600 mg/200 mg	1		1				1				1		
III	900 mg/150 mg	11		4	6			4	4			4	2	2
IV	1200 mg/200 mg	11		5	5			4	4			6	2	2
V	1500 mg/250 mg	3			2	1			2	1			2	1

Patient diagnoses included head/neck (1 patient), esophagus (1), colon (6), pancreas (2), non-small cell lung (1), urethra (1), melanoma (2), sarcoma (3), breast (1), prostate (10) and renal cell (2). No clinical responses have been observed; however, four patients with stable disease have been reported (duration 167-750 days, 3 patients with hormone refractory prostate carcinoma and one with melanoma).

*Phase I evaluation of the "Continuous Schedule" at the University of Wisconsin* 

The second NCI sponsored phase I trial evaluated a loading dose followed by a continuous maintenance dose schedule in 42 patients with advanced cancer. The loading dose was only given in course one, and maintenance dosing continued without a scheduled break (hence the name "continuous schedule"). Cohorts of patients received loading/maintenance doses ranging from 400/50 – 1200/150 mg. In this study, loading doses were split into 4-8 equal doses

# IRB#: 06-044 A(11)

given at 6 hour intervals. Patients received dexamethasone and dolasetron mesylate prior to each dose during the loading period with lorazepam and prochlorperazine prn. Reported severe toxicities for this trial include anorexia, fatigue, dehydration, nausea/vomiting, constipation, diarrhea, elevated liver function tests, and decreased hemoglobin. The MTD and recommended phase II dose for this schedule was 900 mg loading dose (divided into 6 equal doses of 150 mg taken with food q 6 hourly) followed by 100 mg daily maintenance. Among 14 patients treated at the MTD, there were 4 grade 3 events (fatigue in 2 patients, nausea in 1 and vomiting in 1 patient). Subsequently a review of the pharmacokinetics for this study revealed that there was only a minimal increase in plasma concentration between dose level 3 and dose level 4. For this reason the actual doses used in subsequent phase II studies were a loading dose of 600 mg (150 x 4) and a maintenance dose of 100 mg. Among the 12 patients treated at dose level 2 there were 3 patients who experienced grade 3 fatigue and 1 patient with grade 3 nausea. There were no additional grade 3 toxicities recorded as probably due to the drug.

The gastrointestinal toxicities experienced on this protocol are summarized in the following table:

Table 6

NCI Trial II - A Phase I Trial of Perifosine with Different Loading/Maintenance Doses using the "Continuous Schedule" in Patients with Advanced Cancer

			]	Maximum intensity (CTC grade) during any treatment										
Dose	Dosage - Cycle	Patients		course										
Level	1	Treated		Na	usea			Von	niting			Dia	rrhea	
	(Loading /													
	Maintenance)		0	Ι	II	III	0	Ι	II	III	0	Ι	II	III
Ι	400 mg/50 mg	3		3								3		
II	600 mg/50 mg	7		3	3			3	2			3	1	1
	600 mg/100 mg	12		6	2	1		3	2			6	3	
IV	900 mg/100 mg	14		7	3	1		3	2	1		3	3	
V	900 mg/150 mg	6		4	1			4	0			2	3	

Patient diagnoses included pancreatic carcinoma (1 patient), sarcoma (5), colorectal carcinoma (19), ovarian carcinoma (2), renal cell (6), lung cancer (4), esophageal carcinoma (1), breast (1), cervical (1), glioblastoma (1) and tonsilar (1). One partial response in a patient with uterine sarcoma was reported. The responder received 18 cycles of therapy on study and has since been followed for 17 months without significant progression. Seven patients

# IRB#: 06-044 A(11)

had stable disease lasting greater than 2 cycles (renal cell carcinoma -2; sarcoma -2; colon carcinoma -2; ovarian carcinoma -1). [20]

In the phase II program initiated by the National Cancer Institute trials were conducted with both the intermittent and continuous regimens. Preliminary analysis showed that there was greater toxicity associated with the intermittent than the continuous regimen.

#### Table 7

Regimen Intermittent Continuous Number of patients with toxicity data available 87 57 Frequency of: Percent Percent Nausea: 9 Grade 2 36 Grade 3 8 2 Diarrhea: Grade 2 28 4 2 Grade 3 11 Vomiting: Grade 2 45 11 Grade 3 5 2

Toxicity seen in phase II trials conducted by the NCI using either the 'Intermittent' or 'Continuous' Regimens. (See definitions above)

One additional response has been seen in a patient with sarcoma. This occurred in a patient with extra-skeletal myxoid sarcoma who received 10 cycles of therapy on study. [21]

## Perifosine 201

AOI Pharmaceuticals is currently undertaking a phase I/II trial of perifosine in non-small cell lung cancer. In this study patients receive weekly doses in which the total dose is divided into 300 mg doses delivered at least 4 hours apart. Dosing began at 900 mg (300 mg x 3) and was escalated to 1800 mg (300 mg x 6). A dose limiting toxicity was defined as a grade 3 or 4 gastrointestinal toxicity or nausea and/or vomiting lasting more than 48 hours. Two patients at 1800 mg experienced grade 3 diarrhea, and 1500 mg was the maximum tolerated dose. The GI toxicities encountered in the initial 3 cohorts of patients are described in the following table. The table reflects the first week of therapy only.

# IRB#: 06-044 A(11)

Table 8

NRETTERING C

<Sr}ABLISHED

AOI Trial 201 - A Phase I Trial of Perifosine Administered Weekly in Patients with Metastatic Lung Cancer

Dose		Patients	Max	ximur	n inte	ensity	(CTC	C grad	le) du	ring a	ny tre	eatme	nt cou	urse
Level	Dosage - Cycle 1	Treated		Naı	isea			Vom	iting			Diar	rhea	
	(Loading /													
	Maintenance)		0	Ι	II	III	0	Ι	II	III	0	Ι	II	III
Ι	300 mg x 3	5	1	3	1		4	1			2	3		
	weekly													
II	300 mg x 4 weekly	3	2		1		3				1	1	1	
III	300 mg x 5 weekly	5		4	1		1	4			0	3	1	1
IV	300 mg x 6 weekly	4	1	2	1		1	3			0	2		2

## 3.5.3 Pharmacokinetics

The pharmacokinetic data from each of the phase I studies is summarized in the table below.

#### Table 9

Study	Dose Range	Parameter	Median Plasma
			Values (µM)
Study D-21266-3040	100-800 mg/week	Peak Concentration	1.59 – 7.97
		Concentration day 7	0.34 – 2.05
Study D-21266-3079	50 - 350 mg/day	Peak Concentration	3.89 - 14.58
		Concentration Day 22	3.49 - 12.24
Study D-21266-3087	200- 450 mg/week	Peak Concentration	1.51 - 2.42
	(enteric coated)	Steady State Trough	0.54 - 2.00
Intermittent	300/50 - 1500/200	Concentration Day 22	6.87 - 22.31
Continuous	400/50 - 900/150	Concentration Day 2	9.29 - 15.14
		Steady State Concentration	7.23 - 14.36

The phase I pharmacokinetic studies showed that plasma concentrations similar to the IC50 values obtained for many cell lines in *in-vitro* studies could be obtained using each of the regimens with the exception of the enteric coated tablet. When doses above 300 mg were administered at a single time, the pharmacokinetics were not linear. Two patients on the phase I studies responded: one patient on the study that utilized the enteric coated tablets (D-21266-3087) had serum values ranging from  $2.78 - 6.29 \,\mu\text{M}$  and one patient on the continuous regimen had steady state levels of  $12.78 \pm 2.23 \,\mu\text{M}$ .

Nineteen patients with head and neck cancers were enrolled in a phase II trial conducted by a consortium of hospitals in Chicago, and results from this study were presented at the Third Chicago International Symposium on Malignancies of the Chest and Head and Neck. The patients had a median age 59 (range 46-81; 15 were male and 4 female. Five had an ECOG performance status of 0 and the remainder had a status of 1. Thirteen of these patients had received prior chemotherapy and 12 had prior radiotherapy. The continuous regimen was used with a starting dose of 600 mg in 4 divided doses followed by a daily dose of 100mg. The investigators reported that administration by gastrostomy tube was feasible. Grade 3 toxicities described in their presentation included pain in one patient and hypercalcemia in another. Seventeen patients were evaluable for response. There were no objective responses but one patient had stable disease for 4 cycles.

## IRB#: 06-044 A(11)

The only phase II trial of breast cancer enrolled 18 (17 evaluable) patients. This trial was presented at the 2005 San Antonio Breast Cancer Symposium before the study was officially closed. In this trial the intermittent regimen was used. The patients' median age was 52 (range 28-69). There was 1 male patient. The ECOG performance status was 0 for 10, 1 for 6, and 2 for 1 patient. Eight patients had tumors that were ER/PR positive, but none had HER2/neu positive tumors. This was a heavily pre-treated population. Sixteen patients had received prior systemic therapy including neoadjuvant or adjuvant chemotherapy in 11, a single chemotherapy regimen for metastatic disease in 5 patients, and two prior chemotherapy regimens for metastases in 9. Fifteen patients had previously received an anthracycline and 11 a prior taxane. Drug related toxicities included Grade 3 diarrhea (2 patients), vomiting (2 patients), nausea (1 patient) and fatigue (1 patient). One patient had a mixed response after 2 cycles and 2 patients were stable for 4 months. The mixed response occurred in a patient with extensive disease involving multiple organs. At the end of 2 cycles some lesions had shrunk while others had remained stable or increased. Although this patient had experienced no major toxicities, she refused further treatment for unspecified reasons.

# 3.6 Potential impact on metabolism by hepatic enzyme inducing antiepileptic drugs (EIAEDs)

There is increasing evidence that brain tumor patients receiving enzyme-inducing anti-epileptic drugs (EIAEDs) have markedly altered pharmacokinetics, resulting in accelerated drug metabolism. This may result in decreased levels of certain chemotherapeutic agents when administered at conventional doses. Failure to achieve adequate plasma levels of such agents may account for the lack of efficacy in past brain tumor trials.

Perifosine is a potential substrate for the cytochrome P450 system, and the escalating concentrations of perifosine were tested for inhibition of the liver microsomal cytochrome P450 system in vitro (table 10). Enzyme activities associated with CYPIA2 (7-ethoxyresorufin 0-deethylation), CYP2A6 (coumarin 7-hydroxylation), CYP2B6 (S-mephenytoin N-demethylation), CYP2C9 (tolbutamide methyl-hydroxylation), CYP2C19 (S-mephenytoin 4'-hydroxylation), CYP2D6 (dextromethorphan 0-demethylation), CYP2E1 (chlorzoxazone 6-hydroxylation) and CYP3A415 (testosterone 6P-hydroxylation) were determined using enzyme-specific probe compounds incubated with pooled human liver microsomal samples.

In the presence of perifosine, a moderate inhibitory effect was observed on CYP2A6 activity (50%), and a slight inhibitory effect on CYP3A4 activity (29%), in both cases only at the highest concentration (100 yM). No inhibitory effect was observed on CYP2C19 activity by perifosine at any of the concentrations tested.

# IRB#: 06-044 A(11)

Enzyme activities associated with CYPIA2 (7-ethoxyresorufin 0-deethylation), CYP2B6 (S-mephenytoin Ndemethylation), CYP2C9 (tolbutamide methyl-hydroxylation), CYP2D6 (dextromethorphan 0-demethylation), and CYPZEI (chlorzoxazone 6-hydroxylation) were not inhibited by perifosine at any of the concentrations ( $0.25 - 100 \mu M$ ).

Perifosine	Percentage of Activity Remaining							
Conc	CYP1A2	CYP2A6	CYP2B6	CYP2C9	CYP2C19	CYP2D6	CYP2E1	CYP3A4/5
(µM)								
0.0	100.0	100.0	100.0	100.0	100.0	100.0	100.0	100.0
0.25	96.4	97.7	100.1	101.3	98.4	96.0	99.8	102.2
1	101.2	101.2	100.7	96.6	96.8	94.1	100.4	101.3
5	100.8	90.8	100.1	95.7	102.0	98.5	95.8	103.0
10	98.8	94.7	98.0	95.3	97.6	95.9	95.0	97.0
25	99.9	88.9	100.8	96.0	103.1	98.5	96.5	94.5
50	97.8	88.7	101.0	95.8	113.9	94.3	89.1	98.4
100	113.6	46.1	99.9	98.0	106.4	88.1	86.0	71.3

Table 10: The Effect of Perifosine on CYP1A2, CYP2A6, CYP2B6, CYP2C9, CYP2C19, CYP2D6, CYP2E1 AND CYP3SA4/5 Activities in Pooled Human Liver Microsomes

These data suggest that patients taking EIAEDs may have increased drug metabolism and a higher MTD than patients who are not taking EIAEDs. Therefore, to avoid the possibility of effects of EIAEDs on the metabolism of perifosine, and vice-versa, only patients not taking EIAEDs will be eligible for this trial as has become common in trials of novel agents for malignant glioma. (See Appendix 20.2 for a list of EIAED drugs).

## 4.0 OVERVIEW OF STUDY DESIGN/INTERVENTION

## 4.1 Design

Only patients not taking EIAEDs will be considered for this study. If patients were previously on EIAEDs that have been discontinued, patients must have been off the agent for at least 2 weeks prior to registration. For patients who need to start an AED or the AED needs to be changed, it is strongly recommended that all efforts should be made to use a non-EIAED. If another non-EIAED cannot be used, the PI or co-PI should be notified immediately. Questions regarding these requirements should be discussed with PI or co-PI.

## Surgerv

In addition, if cytoreductive surgery is recommended as part of the standard of care for tumor recurrence, all patients will be considered for the "surgical

## IRB#: 06-044 A(11)

arm" of the trial. In this case, patients will receive perifosine for 5-10 days before surgery during which tumor will be aliquoted both for diagnostic purposes and for molecular and pharmacokinetic analyses. Ideally, tissue will be available from a prior surgical resection for intra-patient comparison. Following recovery from surgery, patients will restart perifosine until either tumor progression (as determined by brain imaging with CT or MRI every 2 months) or toxicity. All patients will be followed for overall survival after discontinuing perifosine.

Biologic impact will also be determined by periodic FDG-PET imaging (see below).

#### 4.1.1 Patients will also be stratified as follows:

Histology at Registration:

	GBM/GIosarcoma (GBM/GS) Anaplastic Astrocytoma (AA) Anaplastic Oligodendroglioma (AO) Anaplastic Mixed Glioma (AMG)
Pre-operative Candidate:	Yes or No
Measurable/Evaluable disease:	Yes or No

and Lat

#### 4.2 Intervention

Following a diagnosis of tumor recurrence or progression, all patients will receive perifosine monotherapy until toxicity, progression, or death. Brain imaging (MRI/CT) will be performed at baseline and every 2 months (standard of care). FDG-PET imaging will be performed at baseline, after 1-2 weeks of therapy, and every 4 months to assist with interpretation of tumor response. MR Spectroscopy and MR Perfusion may also be performed with every MRI to assist with interpretation of tumor response. Patients on the surgical arm trial will resume perifosine after recovering from surgery and continue until toxicity, progression, or death.

## 5.0 THERAPEUTIC/DIAGNOSTIC AGENTS

*Perifosine (NSC # 639966; IND # 69,383)* 

Chemical Name: 1,1-dimethyl-4-[[(octadecyloxy)hydroxyphosphinyl]oxy]piperidinium inner salt

Amended: 10/25/11

PR

# IRB#: 06-044 A(11)

Other Names:	Octadecylphosphopiperidine (OPP), D-21266, KRX-0401				
Molecular Formula:	C25H52NO4P				
M.W.:	461.66 g/mol				
CAS No.:	157716-52-4				
How Supplied:	Perifosine is supplied as a film-coated tablet containing 50 mg of active ingredient.				
Storage:	Store closed containers at room temperature (20-25 $^{\circ}$ C). Perifosine is hygroscopic, so containers must be kept closed and dry. Perifosine tablets must be dispensed in the original container.				
Stability:	Stability testing program ongoing. Perifosine has a demonstrated shelf stability of at least 3 years.				
Route of Administration: Oral with meals unless otherwise specified.					
Potential Drug Interactions: None reported.					
Availability:	ifosine is an investigational agent supplied to estigators by AOI Pharmaceuticals.				
Agent Accountability	The Investigator, or a responsible party designated by the Investigator, must maintain a careful record of the inventory and disposition of all agents received from AOI Pharmaceuticals using the Drug Accountability Record Form.				

## 6.1 CRITERIA FOR SUBJECT ELIGIBILITY

## 6.2 Inclusion Criteria

- Patients must have shown unequivocal evidence for tumor progression by MRI or CT scan.
- Patients must be on a stable or decreasing dose of corticosteroids for a minimum of 5 days before the baseline MRI and FDG-PET scans.

# IRB#: 06-044 A(11)

- Patients must have failed prior radiation therapy.
- Patients with prior therapy that included interstitial brachytherapy or stereotactic radiosurgery (including gamma-knife or cyber-knife) must have confirmation of true progressive disease rather than radiation necrosis based upon either PET or Thallium scanning, and/or MR spectroscopy, and/or MR Perfusion, and/or surgical documentation of disease.
- All patients must sign an informed consent indicating that they are aware of the investigational nature of this study. Patients must have signed an authorization for the release of their protected health information.
- Age > 18 years old, and with a life expectancy > 8 weeks.
- Karnofsky Performance Status  $\geq 50\%$
- Patients must have recovered from all acute toxicities from prior therapies. At least 28 days must have elapsed since prior radiation. At least 28 days must have elapsed since prior therapy directed at VEGF/VEGFR such as bevacizumab (Avastin), VEGF-Trap, or AZD2171 In addition, the baseline MRI (with MR Perfusion if possible) and brain FDG-PET scans for this study must also be performed at least 28 days after discontinuation of prior therapy directed at VEGFR. Any questions regarding the definition of anti-VEGF/VEGFR therapy must be discussed with the PI or co-PI.
- Patients must have adequate bone marrow function (WBC >  $3,000/\mu$ l, ANC > 1,500/mm, platelet count of > 100,000/mm, and hemoglobin > 10 gm/dl), adequate liver function (SGOT and bilirubin < 2.5 times ULN), and adequate renal function (creatinine < 1.5 mg/dL before starting therapy. These tests must be performed within 2 weeks prior to treatment initiation. Eligibility level for hemoglobin may be reached by transfusion.
- Baseline MRI (with MR Perfusion if possible) must be performed within 2 weeks prior to treatment initiation. It also must be performed at least 28 days after discontinuation of prior therapy directed at VEGF/VEGFR such as bevacizumab (Avastin), VEGF-Trap, or AZD2171. Any questions regarding the definition of anti-VEGF/VEGFR therapy should be discussed with the PI or co-PI.

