# IRB#: 06-044 A(11)

- Baseline FDG-PET (dedicated study of the brain) must be performed within 2 weeks prior to treatment initiation. It also must be performed at least 28 days after discontinuation of prior therapy directed at VEGF/VEGFR such as bevacizumab (Avastin), VEGF-Trap, or AZD2171. Any questions regarding the definition of anti-VEGF/VEGFR therapy should be discussed with the PI or co-PI.
- There is no limitation on the number of prior relapses or prior therapies.
- Patients must agree to practice adequate contraception. Women of childbearing potential must have a negative B-HCG pregnancy test documented within 7 days prior to registration. Women must not be breast feeding.
- If cytoreductive surgery is planned for tumor recurrence at the time of enrollment, such patients are eligible for the surgical arm, taking perifosine for 5-10 days preoperatively and then continuing perifosine after recovering from the effects of surgery.
- Measurable disease is not required for eligibility in patients who recently underwent resection as long as the following conditions are met as applicable:
  - Progression of disease led to the surgery
  - Gliadel wafers were not placed during the most recent surgery
  - Neither convection enhanced delivery nor catheters for infusion of chemotherapy were used during the most recent surgery
  - Radioactive seeds were not placed during the most recent surgery
  - The histology of the most recent surgery documented recurrent/persistent/progressive malignant glioma

Note, however, that patients who are eligible for surgery because of progressive disease may be considered for the surgical arm.

• Any adult patient with a recurrent/progressive malignant glioma is eligible. Patients will be eligible if the original histology was low-grade glioma and a subsequent histological diagnosis of a high grade (malignant) glioma is made.

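### Confirmation of true progression over radiation necrosis is required only after brachytherapy or radiosurgery; other recently irradiated patients can enter at 28 days with no confirmatory test, and treatment effect could then count towards 6-month PFS

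*Combined protocol and SAP*

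**What the plan says.** All of the entry rules at issue are in the Inclusion Criteria of Section 6.

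- Every patient: "Patients must have shown unequivocal evidence for tumor progression by MRI or CT scan" and "Patients must have failed prior radiation therapy". No measurement threshold, in-field or out-of-field rule, or confirmatory test is attached to the first of these.
- Brachytherapy or radiosurgery only: these patients "must have confirmation of true progressive disease rather than radiation necrosis based upon either PET or Thallium scanning"; MR spectroscopy, MR perfusion and surgical documentation are also accepted.
- Any radiation: "At least 28 days must have elapsed since prior radiation".
- Baseline PET, all patients: "Baseline FDG-PET (dedicated study of the brain) must be performed within 2 weeks prior to treatment initiation". No PET finding is an entry condition. Section 4.2 gives the purpose of the PET series as help in reading response ("every 4 months to assist with interpretation of tumor response"). Section 10.3 adds help in reading the MRI, early metabolic effect and early prediction of response. MR perfusion is done if possible.
- Recently resected patients entering without measurable disease need tissue proof: "The histology of the most recent surgery documented recurrent/persistent/progressive malignant glioma". In the surgical arm, tumor tissue is taken on study (Section 9.5).

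The primary endpoint is 6-month PFS in a single arm (Section 12.0). Progression is measured against the smallest on-study sum, or against baseline if there was no decrease. The Biostatistics section sets the rule for GBM: continue if at least 1 of the first 12 is progression-free at 6 months, and declare the study negative if 3 or fewer of 37 are.

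**The concern.** The protocol accepts that radiation change can look like progression, and for brachytherapy and radiosurgery patients it does not let the MRI or CT reading stand alone. Patients given other radiation, chiefly external beam, face the same imaging standard with only a 28-day interval added. They also have the baseline FDG-PET in hand, but the plan does not use it to confirm eligibility.

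The design makes this matter. There is no control arm to share the error, and progression is judged from the study baseline. A lesion that was treatment effect and did not grow further would therefore be a 6-month success whatever the drug did. With a bar of 4 successes in 37, and 1 in 12 at the first stage, a small number of such patients could change the result.

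**Working it through.** **1. Who is exposed.**

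| Group | Safeguard beyond the MRI/CT reading |
|---|---|
| Prior brachytherapy or radiosurgery | Confirmatory imaging or surgical documentation required |
| Recently resected, no measurable disease | Histology of malignant glioma required |
| Surgical arm | Tumor tissue taken on study |
| Other irradiated patients with measurable or evaluable disease | 28 days since radiation; no confirmatory test |

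The gap is the last row, and within it the patients irradiated recently. The documents do not say how many there will be.

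**2. The plan's own operating characteristics.** Let X1 be successes among the first 12 and X2 among the next 25, each binomial with rate p. Then

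P(positive) = sum over x from 1 to 12 of P(X1 = x) × P(X2 ≥ 4 − x).

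At p = 0.05:
- x = 1: 0.3413 × 0.1271 = 0.0434
- x = 2: 0.0988 × 0.3576 = 0.0353
- x = 3: 0.0173 × 0.7226 = 0.0125
- x ≥ 4: 0.0022

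The sum is 0.0935 from unrounded terms, so P(negative) = 0.9065 against the stated 0.90. At p = 0.20, P(positive) = 0.9024 against the stated minimum of 0.90. The design figures are correct on their own inputs.

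**3. Illustration of contamination.** Two inputs are assumptions, because the documents give neither: f, the share of GBM entrants whose lesion is treatment effect, and q, the 6-month PFS among them. For an inert drug with a true rate of 5%, the apparent rate is

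p = (1 − f) × 0.05 + f × q.

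For example, f = 5% and q = 60% give 0.95 × 0.05 + 0.05 × 0.60 = 0.0775. Putting each p into the formula in step 2 gives P(positive):

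| f | about how many of 37 | q = 30% | q = 50% | q = 60% | q = 70% |
|---|---|---|---|---|---|
| 0 | 0 | 0.0935 | 0.0935 | 0.0935 | 0.0935 |
| 5% | 2 | 0.17 | 0.24 | 0.275 | 0.31 |
| 10% | 4 | 0.26 | 0.41 | 0.484 | 0.55 |

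**4. Sensitivity to the starting rate.** The Biostatistics section reports 15% 6-month PFS for GBM in earlier trials of treatments not thought particularly effective. At p = 0.15, P(positive) is already 0.75. With q = 60%:
- f = 5%: p = 0.95 × 0.15 + 0.05 × 0.60 = 0.1725, P(positive) = 0.84
- f = 10%: p = 0.90 × 0.15 + 0.10 × 0.60 = 0.195, P(positive) = 0.89

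Contamination adds about 0.08 to 0.14 from this start, compared with 0.18 to 0.39 from 5% at the same q.

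**5. Direction.** The shift from 5% is p − 0.05 = f × (q − 0.05). It is upward only if q exceeds 5%. The documents do not give q.

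**The case against.** A reader might infer that external-beam patients enter on any MRI change. The text does not support that: progression must be unequivocal, radiation must have failed, and every patient is seen by a neuro-oncology attending (Section 7.0). An ambiguous early change should not qualify. This stands as a correction, but it does not close the gap. The word has no operational definition, and the same criterion applies to radiosurgery patients, for whom the protocol still asks for confirmation.

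A reader might also infer that the bias can only favour the drug. Nothing in the documents says that treatment effect settles without therapy. Under Section 12.0, a lesion that enlarges by 25%, or a patient who clearly worsens clinically, is scored as progression whatever the cause. Some treatment effect would therefore count as failure. This stands.

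The exposed group is also narrower than all GBM entrants. Prior relapses are unlimited, so some patients may be long past radiation, and resected patients have tissue. This stands too, and it means f should be read as a share of the whole GBM cohort, which may be small.

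Finally, the entry rules of the historical database are not given. If they were similar, its 15% may already contain the same error. That limits a comparison with the historical rate. It does not protect the decision rule, which tests against a fixed 5%.

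**Conclusion.** The point holds in a limited form. Confirmation of true progression is required for one radiation history and not for others, and no other rule I found closes this for recently irradiated, non-surgical patients with measurable or evaluable disease. Treatment effect enrolled as recurrence could be counted as 6-month success. A bias mainly in the drug's favour is plausible, because any such subgroup with 6-month PFS above 5% raises the apparent rate, but neither its size nor its net direction can be established from the documents.

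The probabilities of 0.17-0.31 and 0.26-0.55 rest wholly on assumed f and q and a 5% starting rate. They show how sensitive a 4-of-37 rule is. They are not estimates of this trial's false-positive rate, although a reader might take them as such. If the true background rate is nearer 15%, most of the risk of a positive result comes from the choice of a 5% null, which is a separate matter.

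This is a change the sponsor should make because it is cheap. It is not a flaw that invalidates the design, and the stated sample size is unaffected.

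**What to change.** In the Inclusion Criteria of Section 6, extend the existing confirmation requirement to any patient whose last radiation to the lesion, of whatever type, ended within a window that the sponsor sets and justifies. The accepted evidence can stay as already listed (PET, thallium, MR spectroscopy, MR perfusion or surgical documentation), and the mandatory baseline FDG-PET can serve. The text should state what reading counts as confirmation.

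Record weeks from the end of the last radiation to the start of study drug for every patient. In the Biostatistics section, add a sensitivity result: 6-month PFS in GBM with and without patients inside the window. If the sponsor prefers to leave eligibility as it is, the recorded interval and this row would still show whether the result depends on recently irradiated patients.

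Cost: one eligibility sentence, one data field and one table row. No scan is added where the baseline FDG-PET serves as confirmation, and the sample size does not change. The downside is that a few early post-radiation patients may be deferred.
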